6.7. Patient Disposition

An overview of patient populations will be summarized by treatment group. Frequency counts and percentages of patients excluded prior to randomization by primary reason for exclusion will be provided for patients who failed to meet study entry requirements during screening.

Patient disposition through Week 16 will be summarized using the ITT population. Frequency counts and percentages of patients who complete the study treatment visits or discontinue early from the study along with whether they completed follow-up, did not complete follow-up or enrolled into the extension will be summarized separately by treatment group for patients who are not rescued and for patients who are rescued, along with their reason for study discontinuation. Frequency counts and percentages of patients who complete the treatment or discontinue treatment early will also be summarized separately by treatment group for patients who are not rescued and for patients who are rescued, along with their reason for treatment discontinuation.

A listing of patient disposition will be provided for all randomized patients, with the extent of their participation in the study and the reason for discontinuation. A listing of all randomized patients with their treatment assignment will also be provided.

6.8. Patient Characteristics

Patient characteristics including demographics and baseline characteristics will be summarized descriptively by treatment group for the ITT population. Historical illnesses and pre-existing conditions will be summarized descriptively by treatment group for the ITT population. No formal statistical comparisons will be made among treatment groups unless otherwise stated.

6.8.1. Demographics

Patient demographics will be summarized as described above. The following demographic information will be included:

- Age
- Age group (<65 vs. ≥65)
- Age group (<65, ≥65 to <75, ≥75 to <85, ≥85)
- Gender (male, female)
- Race (American Indian or Alaska Native, Asian, Black or African American, Native Hawaiian or Other Pacific Islander, White, Multiple)
- Region (as defined in [Table JAHM.5.1](#))
- Country
- Weight (kg)
- Weight category (<60 kg, ≥60 to <100 kg, ≥100 kg)
- Height (cm)
- BMI (kg/m²)
- BMI category (<25 kg/m², ≥25 to <30 kg/m², ≥30 kg/m²)

A listing of patient demographics will also be provided for the ITT population.

6.8.2. Baseline Disease Characteristics

The following baseline disease information will be categorized and presented for baseline AD clinical characteristics, baseline health outcome measures, and other baseline demographic and disease characteristics as described above:

- Duration since AD diagnosis (years)
- Duration since AD diagnosis category (0 to <2 years, 2 to <5 years, 5 to <10 years, 10 to <20 years, ≥20 years)
- Age at Diagnosis (years)
- Age Group at Diagnosis (<18 years, ≥18 to <50 years, ≥50 years)
- Habits (Alcohol: Never, Current, Former; Tobacco: Never, Current, Former)
- Skin Infections treated with a pharmacological agent within past year (yes, no, unknown; number if yes)
- Atopic Dermatitis Flares within past year (yes, no, unknown; number if yes)
- Validated Investigator's Global Assessment for AD (IGA) score
- Eczema Area and Severity Index (EASI) score
- SCORing Atopic Dermatitis (SCORAD)
- Body Surface Area (BSA) affected by AD
- Hospital Anxiety Depression Scale (HADS) subscales
- Patient-Oriented Eczema Measure (POEM)
- Itch Numerical Rating Scale (NRS)
- Atopic Dermatitis Sleep Scale (ADSS) Item 2
- Dermatology Life Quality Index (DLQI)
- Skin Pain NRS
- Patient Global Impression of Severity (PGI-S-AD)

- Prior therapy (topical therapy only; systemic therapy)
- Prior use of Cyclosporine (yes, no)
- Cyclosporine inadequate response (yes, no)
- Cyclosporine intolerance (yes, no)
- Cyclosporine contraindication [ineligible] (yes, no)
- Cyclosporine inadvisable (yes no)
- Prior use of TCNI (yes, no)
- TCNI inadequate response (yes, no)
- TCNI intolerance (yes, no)
- TCNI contraindication [ineligible] (yes, no)
- TCNI inadvisable (yes, no)
- Vaccine (yes, no)
- Baseline renal function status: impaired (eGFR <60 mL/min/1.73 m²) or not impaired (eGFR ≥60 mL/min/1.73 m²)
- Immunoglobulin E (IgE): intrinsic(<200 kU/I) or extrinsic (≥200 kU/I)

6.8.3. Historical Illness and Pre-existing Conditions

Historical illnesses are defined as those conditions recorded in the Pre-existing Conditions and Medical History electronic case report form (eCRF) or from the Prespecified Medical History: Comorbidities eCRF with an end date prior to the informed consent date. The number and percentage of patients with selected historical diagnoses will be summarized by treatment group using the ITT population. Historical diagnoses will be categorized using the Medical Dictionary for Regulatory Activities (MedDRA[®], most current available version) algorithmic standardized MedDRA queries (SMQs) or similar pre-defined lists of preferred terms (PTs) of interest.

Preexisting conditions are defined as those conditions with a start date prior to the first dose of the study drug and stop dates that are at or after the informed consent date or have no stop date (i.e., are ongoing). For events occurring on the day of the first dose of study treatment, the date and time of the onset of the event will both be used to determine if the event was pre-existing. Conditions with a partial or missing start date (or time if needed) will be assumed to be ‘not pre-existing’ unless there is evidence, through comparison of partial dates, to suggest otherwise. Pre-existing conditions will be categorized using the MedDRA SMQs or similar pre-defined lists of PTs of interest. Frequency counts and percentages of patients with selected pre-existing conditions will be summarized by treatment group using the ITT population.

6.9. Treatment Compliance

Patient compliance with study medication will be assessed from Week 0 (Visit 2) to Week 16 (Visit 8) or Early Termination using the ITT population.

All patients are expected to take 3 tablets daily from a blister pack as described in the protocol. Each blister pack contains 27 tablets. A patient is considered noncompliant if he or she misses >20% of the prescribed doses during the study, unless the patient’s study drug is withheld by the investigator. For patients who had their treatment temporarily interrupted by the investigator, the period of time that dose was withheld will be taken into account in the compliance calculation.

Compliance in the period of interest up to Visit x will be calculated as follows:

$$\text{Compliance} = \frac{\text{total number of tablets dispensed} - \text{total number of tablets returned}}{\text{expected number of total tablets}}$$

where

- Total number of tablets dispensed: sum of tablets dispensed in the period of interest prior to Visit x ;
- Total number of tablets returned: sum of the tablets returned in the period of interest prior to and including Visit x ;
- Expected number of tablets: number of days in the period of interest*number of tablets taken per day = [(date of last dose – date of first dose + 1) – number of days of temporary drug interruption]*number of tablets taken per day

Patients who are significantly noncompliant (compliance <80%) through Week 16 will be excluded from the PPS population.

Descriptive statistics for percent compliance and non-compliance rate will be summarized for the ITT population by treatment group for Week 0 through Week 16. Sub-intervals of interest, such as compliance between visits, may also be presented. The number of expected doses, tablets dispensed, tablets returned, and percent compliance will be listed by patient for Week 0 through Week 16.

6.9.1. Rescue Treatment

Descriptive statistics for drug accountability of topical low and moderate potency rescue medication provided by the sponsor will also be supplied, including the amount utilized throughout the treatment period. The total amount in grams for low and moderate potency will be summarized between scheduled visits as well as throughout the entire 16 week treatment period.

The dispensed weight of sponsor-provided TCS tubes for the two different potencies (low and moderate) varies between countries due to different supply regions. Average weights of full tubes were used to determine the dispensed weights for each region. Returned tubes were weighed with cap (without the carton) to determine the amount of TCS in grams (g) used at each visit.

For low potency TCS, the dispensed tube weight with cap (without the carton) in Japan is 13.5g. For countries supplied by European distributors (Austria, Hungary, Israel, Poland, Spain, and Switzerland), the dispensed weight of low potency TCS is 21g. The remaining countries, supplied by US distributors (Argentina, Australia, and Republic of Korea), the weight of low potency TCS is 40g.

For moderate potency TCS, the dispensed tube weight with cap (without the carton) in Japan is 13.5g. For countries supplied by European distributors, the dispensed weight of moderate potency TCS is 38g. The remaining countries, supplied by US distributors, the weight of moderate potency TCS is 40g.

Tubes not returned by the end of the study will be marked as one of three options based on patient information: unused, partially used, or fully used. Unused tubes will be considered as weighing the original dispensed amount. Fully used tubes will be considered as weighing the equivalent of an empty tube. Partially used tubes will be considered to be 50% used. If a returned tube is not weighed or not returned then the tube can be classified as partially used, fully used, unused, or unknown. Partially used rescue medication tubes will be defined as 50% used whereas fully used and unused tubes will be defined as 100% and 0% used respectively. When drug accountability is not performed for a particular tube of rescue medication or an answer of 'unknown' is given for a tube which is not returned, that particular tube will not be included in the analysis.

The number of days rescue therapy is used for each patient is also collected on the diary device. The proportion of time that the patients did not use rescue therapy will be summarized for the aforementioned visit intervals by potency (low or moderate) and both potencies combined. For this analysis, the date of the first entry on the diary device will be used to signify the first day of rescue therapy use.

Additionally, a summary of the initial rescue therapy and the reason for requiring initial rescue will be produced, as well as a summary of the proportion of patients rescued at each study visit. A summary of all rescue medications will be provided.

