4.3. Exploratory Objectives

The exploratory objectives of this study are the following:

Objectives/Endpoints

• Mean change from baseline in nocturnal itch assessed by actigraphy device at 1 week and 4 weeks• Frequency of patient-reported “no itch” (Itch NRS score = 0) days from daily diaries from Week 12 to Week 16• Frequency of patient-reported “no pain” (Skin Pain NRS score = 0) days from daily diaries from Week 12 to Week 16• Mean change from baseline in the score of Item 1 of the ADSS at 1 week and 16 weeks• Mean change from baseline in the score of Item 3 of the ADSS at 1 week and 16 weeks• To evaluate changes from baseline in immunoglobulin E levels during the study• To evaluate changes from baseline in eosinophil levels during the study• To characterize baricitinib pharmacokinetics in the AD population and explore relationships between baricitinib exposure and study endpoints• To assess time to 4-pt itch reduction during the first 14 days after initiation of treatment• To assess time to improvement in Skin Pain during the first 14 days after the initiation of treatment• To assess the use of rescue therapy through the weight of sponsor provided topical corticosteroid and number of days not using rescue therapy

5. Study Design

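### Rescue tubes with unknown use drop out of the gram totals, so this rule can only understate topical corticosteroid use, and no bound is planned

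*SAP*

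**What the plan says.** The objective in SAP Section 4.3 is "To assess the use of rescue therapy through the weight of sponsor provided topical corticosteroid and number of days not using rescue therapy". It therefore has two measures, grams and rescue-free days.

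For grams, Section 6.9.1 plans descriptive statistics: "The total amount in grams for low and moderate potency will be summarized between scheduled visits as well as throughout the entire 16 week treatment". Use is found by weighing returned tubes and comparing them with the dispensed weight. The dispensed weight is 13.5 g for both potencies in Japan, 21 g (low) or 38 g (moderate) under European supply, and 40 g for both under US supply.

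Tubes that cannot be weighed follow category rules:

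- Partially used: "Partially used tubes will be considered to be 50% used".
- Fully used or unused: "Fully used tubes will be considered as weighing the equivalent of an empty tube", and later "fully used and unused tubes will be defined as 100% and 0% used respectively".
- Accountability not performed, or an unreturned tube answered as unknown: "that particular tube will not be included in the analysis".

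The section does not say that an excluded tube counts as 0 g. It also does not say whether the patient's total then becomes missing, and it plans no bounding or sensitivity total.

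**The concern.** A total is a sum over tubes. A tube that was dispensed but left out of the sum contributes nothing, as if it had come back unopened. That is one end of the possible range and not a neutral value. The plan already assigns an assumed value, 50%, to tubes known only to be partly used, yet for tubes about which less is known it adopts the minimum without saying so.

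At stake is the gram-based description of rescue use. A reader would take the reported figure as the amount used, when it is a lower limit for tubes with unknown use. The reader would also have no count of excluded tubes from which to judge the shortfall.

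**Working it through.** The SAP states no figure for this point, so there is none to reproduce. The check is direct arithmetic.

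**Inputs.** The tube rules and dispensed weights come from Section 6.9.1. Two quantities are not in the SAP and are assumed over a range: *u*, the share of tubes left out, and *r*, the true mean use of those tubes divided by the mean use of accounted tubes.

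**Step 1: shortfall in the total.** Set mean use of an accounted tube to 1. The reported total is proportional to (1 − u) and the true total to (1 − u) + u·r, so

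shortfall = 1 − (1 − u) / [(1 − u) + u·r].

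At u = 0.20:

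- r = 0.5: 1 − 0.80/0.90 = 11.1%
- r = 1: 1 − 0.80/1.00 = 20.0%
- r = 1.5: 1 − 0.80/1.10 = 27.3%

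| u | r = 0 | r = 0.5 | r = 1 | r = 1.5 |
|---|---|---|---|---|
| 5% | 0% | 2.6% | 5.0% | 7.3% |
| 10% | 0% | 5.3% | 10.0% | 14.3% |
| 20% | 0% | 11.1% | 20.0% | 27.3% |
| 30% | 0% | 17.6% | 30.0% | 39.1% |

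The shortfall is never negative. It is zero only if every excluded tube was in fact unused.

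**Step 2: limit per tube.** One excluded tube can hide at most its dispensed weight less the empty-tube weight: up to 13.5 g (Japan), 21 g or 38 g (European supply, low or moderate potency) or 40 g (US supply), each less packaging. The SAP gives no empty-tube weight.

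**Step 3: comparison between arms.** Take r = 1 and, purely as an illustration, true use of 90 g and 60 g, a difference of 30 g and a ratio of 1.5.

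- 15% unknown in the 90 g arm, 5% in the other: 90 × 0.85 = 76.5 and 60 × 0.95 = 57.0; difference 19.5 g, too small.
- 5% and 15%: 90 × 0.95 = 85.5 and 60 × 0.85 = 51.0; difference 34.5 g, too large.
- 10% in both: 81 and 54; difference 27 g, ratio still 1.5.

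The direction depends on which arm has more unknown tubes and how those were used. The SAP shows neither.

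**Step 4: fully used tubes.** Let W be the dispensed weight and e the empty-tube weight. If a fully used tube weighs e at the end, use is W − e. If it is 100% used and the percentage refers to content, use is again W − e. The two statements differ only if 100% is taken of W, which the SAP does not say.

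**The case against.** The rule covers only a residue. Unweighed or unreturned tubes are first classified as unused, partially used or fully used, and exclusion applies only where that fails; nothing in the SAP suggests that the residue is large. The SAP never says 0 g. Summarising only accounted tubes is a defensible convention for drug-accountability data, and mean imputation rests on an assumption that cannot be tested either. Section 6.9.1 also has a diary-based measure of time without rescue therapy that does not depend on tubes. Grams enter no test in Section 6.6 or Table JAHM.6.5, and the primary censoring rule in Section 6.4 depends on whether rescue occurred, not on how much was used.

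Most of this stands, and it keeps the point minor. It does not remove the one-sided effect on the sum, which follows from the rule whatever the wording intends.

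A reader might infer two stronger points:

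- *That fully used tubes have two conflicting weight rules.* The documents do not support this: one sentence gives the remaining weight, the other the fraction consumed, and they agree on net content. What is missing is a stated base for the percentages and an empty-tube weight.
- *That the difference between placebo and baricitinib is made too small.* The illustration above goes either way once the unknown shares are exchanged, and equal shares with similar use per tube leave the ratio unchanged.

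**Conclusion.** The point holds for the gram totals. As written, the exclusion rule takes the lowest possible value for each tube of unknown use, so it can only understate total TCS use. With 20% of tubes unknown, the total would be about 11% to 27% low for *r* between 0.5 and 1.5. Both quantities are assumed, and with few unknown tubes the effect is small. This takes the rule at its word: the tube is dropped and the patient's remaining tubes are summed. If a patient's total were instead set to missing, the effect would differ, and the SAP does not say so.

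The direction of any distortion between arms cannot be determined from the SAP. The measure is exploratory and descriptive, and no controlled inference is affected.

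**What to change.** Keep the planned summary and add three things to Section 6.9.1:

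1. The number of excluded tubes by treatment arm and potency.
2. A supplementary total in which each excluded tube is imputed at the mean net use of accounted tubes of the same potency and supply region.
3. The same total with every excluded tube set to 0% and then to 100% use, as bounds.

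As clarification only, state that the 50% and 100% rules apply to net content (dispensed weight minus empty-tube weight), and give the empty-tube weights. Also reconcile the sentence that allows three categories for unreturned tubes with the later one that allows four, including unknown.

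The cost is a few lines of SAP text and a short derivation. The downside is a simple imputation assumption, which the bounds cover. No clinical rule and no controlled test changes.

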6.10. Previous and Concomitant Therapy

Summaries of previous and concomitant medications will be based on the ITT population.

At screening, previous and current AD treatments are recorded for each patient. Concomitant therapy for the treatment period is defined as therapy that starts before or during the treatment period and ends during the treatment period or is ongoing (has no end date or ends after the treatment period). Should there be insufficient data to make this comparison (for example, the concomitant therapy stop year is the same as the treatment start year, but the concomitant therapy stop month and day are missing), the medication will be considered as concomitant for the treatment period.

Summaries of previous medications will be as follows:

- Previous AD therapies

Summaries of concomitant medications will be as follows:

- Concomitant medications excluding rescue medicine

6.11. Efficacy Analyses

The general methods used to summarize efficacy data, including the definition of baseline value for assessments are described in Section 6.2. The censoring rules applied to data as well as imputation methods are described in Section 6.4.

[Table JAHM.6.4](#) includes the descriptions and derivations of the primary, secondary, and exploratory efficacy outcomes.

Table JAHM.6.5 provides the detailed analyses including analysis type, method and imputation, population, time point, and comparisons for efficacy analyses.

Table JAHM.6.4. Description and Derivation of Primary, Secondary and Exploratory Efficacy Outcomes

Measure	Description	Variable	Derivation / Comment	Imputation Approach if Missing Components
Validated Investigator's Global Assessment for AD (IGA)	The validated Investigator's global assessment of the patient's overall severity of their AD, based on a static, numeric 5-point scale from 0 (clear) to 4 (severe). The score is based on an overall assessment of the degree of erythema, papulation/induration, oozing/crusting, and lichenification.	▪ IGA score	Single item. Range: 0 to 4 0 represents "clear" 4 represents "severe"	Single item, missing if missing.
		▪ Change from baseline in IGA score	Change from baseline: observed IGA score – baseline IGA score	Missing if baseline or observed value is missing.
		▪ IGA [0,1] with ≥2-point improvement ▪ IGA [0]	
 ▪ Observed score of 0 or 1 and change from baseline ≤-2 ▪ Observed score of 0 	
 ▪ Missing if baseline or observed value is missing. ▪ Single item, missing if missing.
Eczema Area and Severity Index (EASI)	The EASI assesses objective physician estimates of 2 dimensions of atopic dermatitis – disease extent and clinical signs (Hanifin et al 2001) – by scoring the extent of disease (percentage of skin affected: 0 = 0%; 1 = 1-9%; 2 = 10-29%; 3 = 30-49%; 4 = 50-69%; 5 = 70-89%; 6 = 90-100%) and the severity of 4 clinical signs (erythema, edema/papulation, excoriation, and lichenification) each on a scale of 0 to 3 (0 = none, absent; 1 = mild; 2 = moderate; 3 = severe) at 4 body sites (head and neck, trunk, upper limbs, and lower limbs). Half scores are allowed between severities 1, 2 and 3. Each body site will have a score that ranges from 0 to 72, and the final EASI score will be obtained by weight-averaging these 4 scores. Hence, the final EASI score will range from 0 to 72 for each time point.	▪ EASI score	Derive EASI region score for each of head and neck, trunk, upper limbs, and lower limbs as follows: $EASI_{region} = (\text{Erythema} + \text{edema/papulation} + \text{Excoriation} + \text{Lichenification}) * (\text{value from percentage involvement})$ where erythema, edema/papulation, excoriation, and lichenification are evaluated on a scale of 0 to 3 and value from percentage involvement is on a scale of 0 to 6. Then total EASI score is as follows: $EASI = 0.1 * EASI_{head\ and\ neck} + 0.3 * EASI_{trunk} + 0.2 * EASI_{upper\ limbs} + 0.4 * EASI_{lower\ limbs}$	N/A – partial assessments cannot be saved.
		
 ▪ Change from baseline in EASI score ▪ Percent change from baseline EASI score 	Change from baseline: observed EASI score – baseline EASI score % change from baseline: $100 \times \frac{\text{Observed score} - \text{Baseline}}{\text{Baseline}}$	Missing if baseline or observed value is missing.
		▪ EASI50	% Improvement in EASI score from baseline ≥ 50%:	Missing if baseline or observed value is missing.

Measure	Description	Variable	Derivation / Comment	Imputation Approach if Missing Components
			% change from baseline \leq -50	

Measure	Description	Variable	Derivation / Comment	Imputation Approach if Missing Components
		
 EASI75 	% Improvement in EASI score from baseline $\geq 75\%$: % change from baseline ≤ -75	Missing if baseline or observed value is missing.
		
 EASI90 	% Improvement in EASI score from baseline $\geq 90\%$: % change from baseline ≤ -90	Missing if baseline or observed value is missing.
Body Surface Area (BSA) Affected by AD	Body surface area affected by AD will be assessed for 4 separate body regions and is collected as part of the EASI assessment: head and neck, trunk (including genital region), upper extremities, and lower extremities (including the buttocks). Each body region will be assessed for disease extent ranging from 0% to 100% involvement. The overall total percentage will be reported based off of all 4 body regions combined, after applying specific multipliers to the different body regions to account for the percent of the total BSA represented by each of the 4 regions.	
 BSA score 	Use the percentage of skin affected for each region (0 to 100%) in EASI as follows: BSA Total = $0.1 * BSA_{\text{head and neck}} + 0.3 * BSA_{\text{trunk}} + 0.2 * BSA_{\text{upper limbs}} + 0.4 * BSA_{\text{lower limbs}}$	N/A – partial assessments cannot be saved.
		
 Change from baseline in BSA score 	Change from baseline: observed BSA score – baseline BSA score	Missing if baseline or observed value is missing.
SCORing Atopic Dermatitis (SCORAD)	The SCORing Atopic Dermatitis (SCORAD) index uses the rule of nines to assess disease extent (head and neck 9%; upper limbs 9% each; lower limbs 18% each; anterior trunk 18%; back 18%; and genitals 1%). It evaluates 6 clinical characteristics to determine disease severity: (1) erythema,	
 SCORAD score 	SCORAD = $A/5 + 7B/2 + C$, where A is extent of disease, range 0-100 B is disease severity, range 0-18 C is subjective symptoms, range 0-20	Missing if components A and B are missing or if component C is missing. Partial assessments performed by physician cannot be saved and partial assessments performed by subject cannot be saved.

Measure	Description	Variable	Derivation / Comment	Imputation Approach if Missing Components
	(2) edema/papulation, (3) oozing/crusts, (4) excoriation, (5) lichenification, and (6) dryness on a scale of 0 to 3 (0=absence, 1=mild, 2=moderate, 3=severe). The SCORAD index also assesses subjective symptoms of pruritus and sleep loss in the last 72 hours on visual analogue scales (VAS) of 0 to 10 where 0 is no itch or sleep loss and 10 is worst imaginable itch or sleep loss. These 3 aspects: extent of disease, disease severity, and subjective symptoms combine to give a maximum possible score of 103 (Stalder et al. 1993; Kunz et al. 1997; Schram et al. 2012).	
 ▪ Change from baseline in SCORAD score ▪ Percent change from baseline in SCORAD score 	Change from baseline: observed SCORAD score – baseline SCORAD score % change from baseline: $100 \times \frac{\text{Observed score} - \text{Baseline}}{\text{Baseline}}$	Missing if baseline or observed value is missing.

 ▪ SCORAD75 		% Improvement in SCORAD from baseline $\geq 75\%$: % change from baseline ≤ -75	Missing if baseline or observed value is missing.	

 ▪ SCORAD90 		% Improvement in SCORAD from baseline $\geq 90\%$: % change from baseline ≤ -90	Missing if baseline or observed value is missing.	

Table JAHM.6.5. Description of Primary, Secondary and Exploratory Efficacy Analyses

Measure	Variable	Analysis Method (Section 6.2.3)	Population (Section 6.2.1)	Comparison/Time Point	Analysis Type
Validated Investigator's Global Assessment for AD (IGA)	Proportion of patients achieving IGA [0,1] with a ≥ 2 -point improvement	Logistic regression using NRI	ITT	Bari 4-mg or Bari 2-mg vs PBO; Week 16	Primary analysis
				Bari 1-mg vs PBO; Week 16	Key secondary analysis
			PPS	Bari 4-mg or Bari 2-mg or Bari 1-mg vs PBO; Week 16	Sensitivity analysis
		ITT	Bari 4-mg or Bari 2-mg or Bari 1-mg vs PBO; Week 4	Secondary analysis	
		Logistic regression using pMI and Tipping Point	ITT	Bari 4-mg or Bari 2-mg or Bari 1-mg vs PBO; Week 16	Sensitivity analysis
	Proportion of patients achieving IGA [0]	Logistic regression using NRI	ITT	Bari 4-mg or Bari 2-mg or Bari 1-mg vs PBO; Week 16	Secondary analysis
Eczema Area and Severity Index (EASI)	
 EASI score Change from baseline in EASI score Percent change from baseline in EASI score 	MMRM	ITT	Bari 4-mg or Bari 2-mg or Bari 1-mg vs PBO; Week 16	Key secondary analysis
			PPS	Bari 4-mg or Bari 2-mg or Bari 1-mg vs PBO; Week 16	Sensitivity analysis
		ANCOVA using mLOCF	ITT	Bari 4-mg or Bari 2-mg or Bari 1-mg vs PBO; Week 16	Sensitivity analysis
		pMI and Tipping Point	ITT	Bari 4-mg or Bari 2-mg or Bari 1-mg vs PBO; Week 16	Sensitivity analysis
	
 Proportion of patients achieving EASI50 Proportion of patients achieving EASI75 Proportion of patients achieving EASI90 	Logistic regression using NRI	ITT	Bari 4-mg or Bari 2-mg or Bari 1-mg vs PBO; Week 16	Secondary analysis
			ITT	Bari 4-mg or Bari 2-mg or Bari 1-mg vs PBO; Week 16	Key secondary analysis
		Logistic regression using NRI	PPS	Bari 4-mg or Bari 2-mg or Bari 1-mg vs PBO; Week 16	Sensitivity analysis
			pMI and Tipping Point	ITT	Bari 4-mg or Bari 2-mg or Bari 1-mg vs PBO; Week 16
		Body Surface Area (BSA) Affected by AD	
 BSA score Change from baseline in BSA score 	MMRM	ITT
ANCOVA using mLOCF	ITT			Bari 4-mg or Bari 2-mg or Bari 1-mg vs PBO; Week 16	Sensitivity analysis

Measure	Variable	Analysis Method (Section 6.2.3)	Population (Section 6.2.1)	Comparison/Time Point	Analysis Type
SCORing Atopic Dermatitis (SCORAD)	
 • SCORAD score • Change from baseline in SCORAD score 	MMRM	ITT	Bari 4-mg or Bari 2-mg or Bari 1-mg vs PBO; Week 16	Secondary analysis
		ANCOVA using mLOCF	ITT	Bari 4-mg or Bari 2-mg or Bari 1-mg vs PBO; Week 16	Sensitivity analysis
	Proportion of patients achieving SCORAD75	Logistic regression using NRI	ITT	Bari 4-mg or Bari 2-mg or Bari 1-mg vs PBO; Week 16	Key secondary analysis
			PPS	Bari 4-mg or Bari 2-mg or Bari 1-mg vs PBO; Week 16	Sensitivity analysis
		Logistic regression using pMI	ITT	Bari 4-mg or Bari 2-mg or Bari 1-mg vs PBO; Week 16	Sensitivity analysis
	Proportion of patients achieving SCORAD90	Logistic regression using NRI	ITT	Bari 4-mg or Bari 2-mg or Bari 1-mg vs PBO; Week 16	Secondary analysis
		pMI and Tipping Point	ITT	Bari 4-mg or Bari 2-mg or Bari 1-mg vs PBO; Week 16	Sensitivity analysis
Skin Infections	Proportion of patients developing skin infections requiring antibiotic treatment	Fisher's exact	ITT	Bari 4-mg or Bari 2-mg or Bari 1-mg vs PBO; Week 16	Secondary analysis

Abbreviations: ANCOVA = analysis of covariance; Bari = baricitinib; ITT = intent-to-treat; mLOCF = modified last observation carried forward; MMRM = mixed model repeated measures; NRI = nonresponder imputation; PBO = placebo; pMI=placebo multiple imputation; PPS = per protocol set..

